3.1.2. Missing data

Subjects may have missing specific data points for a variety of causes. In general, data may be missing due to a missed visit, non-evaluability of a specific clinical measurement at its planned clinical visit or a subject's early withdrawal from study. The general procedures outlined below describe what will be done when a data point is missing.

3.1.2.1. *Imputations of missing data*

Generally, only evaluable measurements are considered for the analyses. No values are imputed for missed or non-evaluable visits. In case of primary and secondary efficacy endpoints possible specific requirements are stated in the according analysis sections.

3.1.2.2. *Partial Dates*

Partially incomplete dates (day or day/month missing) will be imputed for dates of progression as well as for therapy begin and/or end dates. Completely missing dates and missing years will not be imputed.

Imputation Rules for Partial Progression Dates

	Missing	Impute	Exception
Event Date	Day	01	Default to Day 1 of the study if an event started the same year and month as Day 1
	Day /Month	01JAN	Default to Day 1 of the study if an event started the same year as Day 1

Imputation Rules for Partial Therapy Start and Stop Dates

	Missing	Impute	Exception
Start date	Day	01	Default to Day 1 of the study if a therapy started the same year and month as Day 1
	Day /Month	01JAN	Default to Day 1 of the study if a therapy started the same year as Day 1
Stop date	Day	Last day of the month	Default to the EOS date if the imputed therapy stop date is after the EOS date
	Day/Month	31Dec	

3.1.3. Stratification errors

Stratification errors are defined as different values in the stratification factors compared between the randomization system and actual patient values from the electronic case report forms (eCRF).

Stratified analyses that are intended to evaluate the treatment effect will be based on the randomized stratum. If stratification error for a factor includes more than 10% of value, actual value instead of randomized stratum will be used in analysis.

Covariate analyses will be based on subject's actual values.

3.2. Types and time points of analyses

3.2.1. Primary analysis

Primary analysis will be performed after last patient, last visit (LPLV) and subsequent data cleaning.

3.3. Definition of populations for analyses

3.3.1. Intention-to-Treat (ITT) population

Primary and secondary analyses will be based on the Intention-to-Treat (ITT) population; that is, all patients who were included in the randomization. All subjects will be analyzed according to the therapy arm to which they have been randomized. Subjects who terminate the study before their scheduled final study visits will be censored.

3.3.2. QoL population

Data from QoL questionnaires will be analyzed for all the patients which filled baseline or at least on after baseline questionnaire.

3.3.3. Per-Protocol (PP) population

No analysis on Per-Protocol (PP) population will be preformed

3.4. Study population

3.4.1. Patient status

Absolute and relative frequencies of patient status will be tabulated for both therapy arms in terms of patient randomized, patient undergone surgery, end-of-study reasons and cause of deaths.

3.4.2. Protocol deviations

Important protocol deviations were defined with respect of violations of against the inclusion/exclusion criteria, stratification errors and all deviations from protocol of the study, eg. Local therapy, surgery and/or radiotherapy in arm B or surgery of metastases in both arms.

Summaries of IPDs will be presented per treatment arm and in total. Additionally, patient listings will be given.

3.4.3. Baseline demographic and disease characteristics

Demographic and tumour characteristics data at baseline will be summarized descriptively per treatment arm and in total. Demographic and anamnestic data at baseline include age, height, weight, menopausal status, tumour stage, nodal status, tumour grade, HER2-status and hormone receptor status (estrogen and progesterone).

3.4.4. Treatment and study information

Exposure during study will be given for local (surgery and/or radiation) as well for systematic therapies. Systematic therapies will be listed per patient.

Surgery type and tumour classification after surgery will be summarized descriptively.

Information on treatment violations will be presented descriptively per treatment arm and in total.

3.5. Primary endpoint evaluation

3.5.1. Primary endpoint

Median survival time will be compared through overall survival. Overall survival (OS) is determined by the time from randomization to death including breast cancer-related deaths and deaths from any other cause. If the patient is alive at the end of the observation period, the patient will be censored.

The null and alternative hypotheses for the primary endpoint are as follows:

- H0: Overall survival is equal in patients receiving local therapy (surgery) compared to patients receiving no local therapy (surgery on demand)
- H1: Overall survival differs between patients receiving local therapy (surgery) compared to patients receiving no local therapy (surgery on demand)
-

3.5.2. Data set for primary endpoint

Data analysis for the primary endpoint will be based on the ITT-population. Subjects who terminate the study before their scheduled final study visits will be censored at the time of their last contact.

3.5.3. Efficacy analysis for primary endpoint

For the primary endpoint, a *2-sided log-rank* test (unstratified) will be used to test for differences between local therapy versus no local therapy at an overall alpha level of 0.05.

3.5.4. Sensitivity analyses for primary endpoint

A stratified version of the 2-sided log-rank test will be performed with the stratification factors used for randomization except geographic region. Kaplan-Meier curves and estimates will be provided for each treatment group. Potential confounding effects of the impact of other variables (grading, age, her2-neu expression and so on) will be assessed with the *multiple Cox-Regression analysis*.

3.6. Secondary endpoint evaluation

3.6.1. Secondary endpoints

- Time to distant progression (TTPd)
- Time to local progression (TTPl)

- data from QoL questionnaires
- Reduction of growth factors, circulating tumor cells, stem cells in pre-selected centers

Time to distant progression (TTPd) is defined by the time from randomization to first distant progression. Progression event is defined as a detection of “new” lesions (i.e., newly detected metastases, in a new or pre-existing metastatic site) or progression of existing metastases (i.e., those present at baseline). Distant progression is a progression in location different than breast (localization mamma, chest wall or axilla). Local progression before distant occurrence will be ignored.

Time to local progression (TTPl) is defined by the time from randomization to first local recurrence. Local recurrence is defined as recurrence in breast with localization mamma, chest wall or axilla.

Data from QoL will be assessed using the EORTC QLQ-C30 and the modified QLQ-BR23. Hence, this endpoints are the scores (of the base questionnaire and of the supplementary breast cancer module) described in the scoring procedures.

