Based on these assumptions and taking into consideration a potential drop-out rate of 5%, 254 patients (127 in each treatment arm) need to be enrolled in order to observe 192 events which should be sufficient to yield 80% power for a two-sided log-rank test at an overall alpha level of 5%.

In order to control the overall type one error at the 5% level, the interim analyses will follow a Lan-DeMets alpha spending approach, using an O'Brien-Fleming boundary function. According to this approach, the study will be stopped after 50% of the total number of events (96 events) due to efficacy (median survival in experimental arm greater than in the control arm) or due to futility (median survival in experimental arm less than in the control arm) at a 2-sided alpha = 0.00306.

Secondary endpoints

Time to distant progression (TTPd)

Time to treatment change due to systemic progression.

Time to local progression (TTPI)

Increase in size >25% of the primary tumor in arm B (no local therapy).
Local recurrence in arm A (local therapy).

For the secondary endpoint, TTPd and TTPI, the *2-sided log-rank test* (unstratified) will be used to test for differences between local versus no local therapy at an overall alpha level of 5%. A stratified version of the 2-sided log-rank test will be performed

with the stratification factors used for randomization except geographic region. Kaplan-Meier curves and estimates will be provided for each treatment group. The multiple analysis will be conducted with a *Cox regression model*. The local recurrence in arm A (local therapy) will be assessed with *univariate and multiple logistic regression analysis*.

Reduction of growth factors, circulating tumor cells, stem cells in pre-selected centers

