Appendix 4: Follow up Flowchart

recommended Assessments & Investigations	YEAR 1				YEAR 2				YEAR 3		YEAR 4		YEAR 5		RELAPSE/PROGRESSION	
	3	6	9	12	15	18	21	24	30	36	42	48	54	60		
Months (± 1 month)	3	6	9	12	15	18	21	24	30	36	42	48	54	60		
History and Clinical Examination																
Intercurrent Medical History	•	•	•	•	•	•	•	•	•	•	•	•	•	•	•	
General and Physical Examination	•	•	•	•	•	•	•	•	•	•	•	•	•	•	•	
Quality of Life		•		•		•		•		•		•		•		
Laboratory (incl CEA, CA 15-3)	According to systemic therapy but at least every 2-4 months										every 5-7 months					
Imaging																
Breast Imaging (check guidance)	(○)	(○)	(○)	•	(○)	(○)	(○)	•	(○)	•	(○)	•	(○)	•	•	
CT ¹ Thorax/Abdomen (US/chest X-ray)	•	•	•	•	•	•	•	•	•	•	•	•	•	•	•	
Bone Imaging	In cases of pre-randomized diagnosed bone metastases every 2-4 months, in case of suspected bone metastases for staging								In cases of pre-randomized diagnosed bone metastases every 5-7 months, in case of suspected bone metastases for staging							
Pregnancy Test ²	in pre/perimenopausal women according to local policy															

¹ Alternatively a PET-CT scan can be performed

² Pregnancy tests have to be performed in pre/perimenopausal women during screening phase and at regular intervals throughout the trial according to local policy

Appendix 5: EORTC QLQ-C30 (version 3.0), QLQ BR 23

GERMAN

EORTC QLQ-C30 (version 3.0)

Wir sind an einigen Angaben interessiert, die Sie und Ihre Gesundheit betreffen. Bitte beantworten Sie die folgenden Fragen selbst, indem Sie die Zahl ankreuzen, die am besten auf Sie zutrifft. Es gibt keine "richtigen" oder "falschen" Antworten. Ihre Angaben werden streng vertraulich behandelt.

Bitte tragen Sie Ihre Initialen ein:

--	--	--	--

Ihr Geburtstag (Tag, Monat, Jahr):

--	--	--	--	--	--

Das heutige Datum (Tag, Monat, Jahr):

31					
----	--	--	--	--	--

	Überhaupt			
	nicht	Wenig	Mäßig	Sehr
1. Bereitet es Ihnen Schwierigkeiten sich körperlich anzustrengen (z.B. eine schwere Einkaufstasche oder einen Koffer zu tragen?)	1	2	3	4
2. Bereitet es Ihnen Schwierigkeiten, einen längeren Spaziergang zu machen?	1	2	3	4
3. Bereitet es Ihnen Schwierigkeiten, eine kurze Strecke außer Haus zu gehen?	1	2	3	4
4. Müssen Sie tagsüber im Bett liegen oder in einem Sessel sitzen?	1	2	3	4
5. Brauchen Sie Hilfe beim Essen, Anziehen, Waschen oder Benutzen der Toilette?	1	2	3	4

Während der letzten Woche:

	Überhaupt			

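### SAP 3.6.1 leaves the protocol's arm B event, growth of the primary by more than 25%, out of time to local progression, and SAP Section 5 does not list the change

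*SAP*

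**What the plan says.** **Protocol, Outcome measurements and statistical analyses, Secondary endpoints.** TTPl has a separate event in each arm. For arm B it is "Increase in size >25% of the primary tumor in arm B (no local therapy"; for arm A it is local recurrence. The same section treats recurrence as an arm A outcome with its own analysis: "The local recurrence in arm A (local therapy) will be assessed with" univariate and multiple logistic regression. Time to distant progression (TTPd) is "Time to treatment change due to systemic progression".

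**SAP 3.6.1.** "Time to local progression (TTPl) is defined by the time from randomization to first local recurrence". The next sentence reads: "Local recurrence is defined as recurrence in breast with localization mamma, chest wall or axilla". There is no size criterion and no rule specific to arm B. TTPd now runs from randomisation to first distant progression, counting new lesions and also progression of metastases already present at baseline. The TTPd paragraph adds: "Local progression before distant occurrence will be ignored".

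**SAP 3.6.2, 3.6.3 and 4.3.** TTPl is compared between arms in the ITT population by log-rank test (table 10), stratified log-rank test (table 12) and Cox model (table 14).

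**SAP 5.** The only listed departure from the protocol is stratification by centre instead of geographic region.

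**Protocol Appendix 4.** Among the recommended assessments is "Breast Imaging (check guidance", and one column is headed "RELAPSE/PROGRESSION".

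**The concern.** Arm B keeps its primary by design, so growth of that primary is the main way in which an arm B patient fails locally. A definition built on recurrence alone has no place for it. A programmer who follows SAP 3.6.1 as written would count local failure after resection in arm A and would not count growth of the intact tumour in arm B.

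Local time to progression is part of the first secondary objective (SAP 2.2.2). The conclusion on local control would then depend on how much arm B growth happened to be recorded as recurrence, which the SAP does not fix. Because Section 5 is silent, a reader of the report would not know that the endpoint differs from the protocol's.

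**Working it through.** **1. Definitions side by side**

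| | Protocol | SAP 3.6.1, read literally |
|---|---|---|
| Arm A event | Local recurrence | Local recurrence in breast, chest wall or axilla |
| Arm B: growth of primary >25% | Counts | Not mentioned |
| Arm B: new breast, chest-wall or axillary lesion | Not mentioned | Might be recorded as recurrence |
| Listed in SAP 5 | – | No |

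Arm A is essentially unchanged. Arm B loses one event type and may gain another.

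**2. Direction.** Let a be the arm A events and b the arm B events under the protocol. Let L be the growth events lost and m the arm B events that only the SAP counts. The SAP's arm B count is b' = b - L + m. With equal numbers at risk, half the events are expected in each arm, and the log-rank statistic is approximately

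z = (a - b) / √(a + b), positive meaning against surgery.

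Its derivative in b is -(3a + b) / [2(a + b)^1.5], which is always negative. With a fixed, z therefore rises when b' < b, that is, when L > m. If m > L, it falls.

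With a = 5 (assumed):

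| Arm B events | z | two-sided p |
|---|---|---|
| 24 | -3.53 | 0.0004 |
| 12 | -1.70 | 0.090 |
| 6 | -0.30 | 0.76 |
| 3 | +0.71 | 0.48 |
| 0 | +2.24 | 0.025 |

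If the arm B count instead rose to 30, z would be (5 - 30)/√35 = -4.23, a shift towards surgery.

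**3. Size, as illustration only.** From the documents: 127 patients per arm, 48-month accrual, end at month 108, median survival 36 v 24 months. Assumed: every local event rate, exponential times, and death censoring local events. The local hazard is the death hazard × p/(1 - p) for crude incidence p. The test is a two-sided log-rank at |z| > 1.96, with 5000 runs per row. Cells show % of runs significantly for / against surgery.

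| Arm B rate recorded | Mean z (A 5%, 36 v 24) | A 5%, 36 v 24 | A 10%, 36 v 24 | A 5%, 24 v 24 |
|---|---|---|---|---|
| 20% (all growth counted) | -4.59 | 99.8 / 0 | 94.2 / 0 | 97.3 / 0 |
| 10% | -2.30 | 63.8 / 0 | 16.6 / 0.1 | 31.5 / 0 |
| 5% | -0.70 | 10.3 / 0.3 | 0.7 / 8.3 | 2.3 / 2.3 |
| 3% | +0.18 | 1.5 / 3.1 | 0 / 29.4 | 0.4 / 10.6 |
| 0% | +1.94 | 0 / 50.7 | 0 / 96.4 | 0 / 79.0 |

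With arm A at 5% there are about 5 arm A events. Arm B at 20% gives about 24.

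**4. A second set of assumed rates (24-month risks, 1000 runs).** Take arm A recurrence at 10% and arm B growth at 30%. The protocol definition gives about 20 v 42 events and mean z about -4.6. The literal SAP gives about 20 v 0 events and z about +4.2 with no arm B recurrences, or about 20 v 8 and z about +1.8 with arm B recurrences at 5%. With arm A at 5% instead, z goes from -6.2 under the protocol to about 0 when arm B recurrences are 5%. The shift persists, but the sign need not reverse.

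**5. The plan's own figure.** The documents give no event count or power for TTPl. The 192 deaths planned for overall survival reproduce (191 by Schoenfeld's formula at hazard ratio 0.666; power 80.4% with 192), but they have no bearing here.

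**The case against.** The strongest reply is that nothing was meant to change. The endpoint is still called time to local progression, the SAP says that it is based on the protocol, and its TTPd paragraph speaks of local progression. Appendix 4 puts relapse and progression in one column. On this view recurrence is loose wording, the protocol's event still applies, and Section 5 had nothing to list. This may be so. But the SAP does not say it, and SAP 3.6.1 does write a rule for growth of baseline disease at distant sites while writing none for the breast.

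A second reply concerns direction, and it stands. A reader might infer that the SAP certainly biases TTPl against surgery, or that it turns a benefit into a significant harm. The documents support neither. The literal SAP can count arm B chest-wall, axillary or new breast lesions that the protocol does not. If recurrence loosely means any local progression, there is no 25% threshold, arm B events could increase, and the shift could favour surgery. The most striking percentages in the table need almost no recorded arm B events, and all of them rest on assumed rates.

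Third, the protocol definition is not a neutral benchmark, since it sets growth of an intact tumour against recurrence after resection. That also stands. It limits how TTPl can be interpreted but does not excuse an unlisted change.

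**Conclusion.** The point holds. SAP 3.6.1 omits the protocol's arm B event, does not say whether growth of an unresected primary counts, and Section 5 lists neither this nor the change in TTPd from time to treatment change to first distant progression. The effect of the TTPd change was not assessed.

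On the literal reading, and provided the lost growth events outnumber the arm B events that the SAP adds, the ITT log-rank and Cox comparison of TTPl shifts against surgery relative to the protocol definition. The size of the shift, and whether the sign reverses, cannot be derived from the documents. Overall survival is unaffected. This should be fixed before the TTPl analysis is run, as a matter for a secondary endpoint.

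**What to change.** 1. In SAP 3.6.1, state the protocol's arm B event, growth of the primary by more than 25%, alongside local recurrence in arm A. Name the reference measurement, which the protocol does not give. Say whether growth of axillary disease present at baseline counts; neither document does.
2. If the sponsor prefers one definition for both arms, it could be the first of growth of an unresected primary by more than 25%, or a recurrence or new lesion in breast, chest wall or axilla. This is a new composite, so list and justify it in Section 5.
3. List the TTPd change in Section 5.
4. State in the report that growth of an intact tumour and recurrence after resection are different event types.
5. Confirm that primary size was recorded at follow-up. Appendix 4 only recommends breast imaging, with a full mark at months 12, 24, 36, 48 and 60 and at relapse or progression, and a bracketed mark at other visits. The protocol's Follow up section does not list it. If size was not recorded, say so and do not interpret the between-arm TTPl test as a comparison of local control.

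The cost is SAP wording and one derivation, provided size data exist. The restored endpoint would still mix two unlike event types across the arms.

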3.6.2. Data set for secondary endpoints

Data analysis for the secondary endpoint time to distant progression and time to local progression will be based on the ITT-population.

Data from QoL questionnaires will be analyzed for all the patients which filled baseline or at least on after baseline questionnaire.

Reduction of growth factors, circulating tumor cells, stem cells will be analyzed on all evaluable data from pre-selected centers.

3.6.3. Efficacy analyses for secondary endpoints

Difference in time to distant progression and time to local progression between local therapy versus no local therapy will be estimated through 2-sided log-rank

With respect to analysis of QoL endpoints the mean change of the linear transformed scores from baseline (and 95% CI using the normal approximation) will also be assessed. Line charts depicting the mean changes (and standard errors) of items and subscales over time will be provided for each treatment arm from the baseline assessment.

Completion and compliance rates will be summarized at each time point by treatment arm with reasons for missing data.

Reduction of growth factors, circulating tumor cells, stem cells in pre-selected centers will be defined in later version of SAP in an efficient amount of data will be available.

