3.9. Covariates

To adjust for the possible effect of demographic or prognostic factors multivariate analyses will be performed. To avoid multi-collinearity between the covariates, prior correlation analyses will be performed. Depending on the statistical results and the clinical relevance, highly correlated covariates may be excluded from multivariate analyses. Binary dependent variables will be analyzed using logistic regression models. Metric dependent variables will be analyzed using general linear models or a non-parametric equivalent if appropriate. Forest plots will be given where appropriate.

The following variables are candidates for covariates which will be used for analyses to explore the relationship to the primary and secondary endpoints:

- Age group*
- T-stage
- N-stage
- Histologic grade
- Hormone Receptor status*
- HER2 status*
- Tumor Subtype

- Endocrine therapy
- Chemotherapy
- Immunotherapy
- Location of metastases

*Based on patient's actual value (eCRF)

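### Quality of life is a secondary endpoint, but the SAP names no baseline-adjusted between-arm difference, and the protocol's questionnaire schedules conflict

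*SAP*

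**What the plan says.** SAP 2.2.2 makes quality of life in the two arms the fourth secondary objective. SAP 3.6.1 lists it as a secondary endpoint and states that "this endpoints are the scores (of the base questionnaire and of the supplementary breast cancer module) described in the scoring procedures".

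SAP 3.6.3 gives three QoL outputs:
- For the scores: "the mean change of the linear transformed scores from baseline (and 95% CI using the normal approximation) will also be assessed"
- Charts by arm showing how items and subscales move away from baseline, with standard errors.
- For questionnaire return: "Completion and compliance rates will be summarized at each time point by treatment arm with reasons for missing data"

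For the progression endpoints the same section does name an arm comparison: "Difference in time to distant progression and time to local progression between local therapy versus no local therapy will be estimated through 2-sided log-rank".

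SAP 3.6.2 sets the analysis population: "Data from QoL questionnaires will be analyzed for all the patients which filled baseline or at least on after baseline questionnaire". SAP 3.1.2.1 imputes nothing for missed visits. SAP 3.9 adds that "Metric dependent variables will be analyzed using general linear models or a non-parametric equivalent if appropriate" and introduces its covariates with "The following variables are candidates for covariates which will be used for analyses to explore the relationship to the primary and secondary endpoints". The SAP's list of planned tables and figures (section 4) contains no QoL output. The protocol's statistical section gives methods for survival, progression and the laboratory markers, but none for QoL.

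The protocol describes the QoL visits in three places:
- **Study design:** a form at baseline, then six-monthly from enrolment, ending at month 42.
- **Follow up:** a form at baseline, then six-monthly counted from treatment up to month 24, then yearly up to month 48.
- **Appendix 4 flowchart:** marks at months 6, 12, 18, 24, 36, 48 and 60, reading the row by column position.

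The SAP refers to time points but does not list them.

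**The concern.** An objective about QoL in both arms of a randomised trial calls for a comparison of the arms. The SAP's QoL text stops at change from baseline and displays by arm. The reader must derive the difference and its interval. The derived version is the unadjusted change-score difference, which is less precise than one that uses the baseline score as a covariate, although those scores are already collected.

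The visit schedule is a separate matter of consistency. Which forms a site hands out after month 24 depends on which protocol section it follows. The planned completion rates need a count of forms due, and at the disputed months that count is not defined.

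**Working it through.** **No QoL planning figure to reproduce.** The documents give no QoL effect size, standard deviation, correlation or power. The check therefore has three parts: what the SAP names, what baseline adjustment would gain, and how the schedules compare.

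**1. What the SAP names**

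| Element | TTPd and TTPl | QoL |
|---|---|---|
| Arm difference named in 3.6.3 | yes | no |
| Baseline value used | not applicable | by subtraction only |
| Model in 3.9 | not needed for this point | generic linear model; no arm term named |
| Baseline score among 3.9 candidates | not applicable | no |

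The 3.9 candidates are age group, T-stage, N-stage, grade, hormone receptor status, HER2 status, tumour subtype, endocrine therapy, chemotherapy, immunotherapy and location of metastases.

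**2. Gain from baseline adjustment**

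Assume equal variance s² at baseline and follow-up, and correlation ρ between them.
- Change-score difference: variance = 2(1 − ρ)s²(1/nA + 1/nB)
- ANCOVA difference: variance = (1 − ρ²)s²(1/nA + 1/nB)
- Ratio, ANCOVA to change score = (1 − ρ²) / [2(1 − ρ)] = (1 + ρ)/2

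| Assumed ρ | Variance ratio | CI width ratio (square root) | CI narrower by |
|---|---|---|---|
| 0.3 | 0.65 | 0.81 | 19% |
| 0.5 | 0.75 | 0.87 | 13% |
| 0.7 | 0.85 | 0.92 | 8% |

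To put this on an absolute scale, take 127 patients per arm and the design medians of 36 months (arm A) and 24 months (arm B) from the protocol's sample size section. Assume exponential survival, no dropout and a form from every survivor. The numbers alive are 127 × 2^(−t/36) and 127 × 2^(−t/24).
- Month 24: 80.0 and 63.5. Then 1.96 × √(1/80.0 + 1/63.5) = 0.329.
- Month 48: 50.4 and 31.8. Then 1.96 × √(1/50.4 + 1/31.8) = 0.444.

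Multiplying by √[2(1 − ρ)] or √(1 − ρ²) gives the 95% CI half-width in SD units:

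| | ρ = 0.3 | ρ = 0.5 | ρ = 0.7 |
|---|---|---|---|
| Month 24, change score | 0.39 | 0.33 | 0.26 |
| Month 24, ANCOVA | 0.31 | 0.29 | 0.24 |
| Month 48, change score | 0.53 | 0.44 | 0.34 |
| Month 48, ANCOVA | 0.42 | 0.38 | 0.32 |

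**3. Schedules side by side (post-baseline months)**

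| Source | 6, 12, 18, 24 | 30 | 36 | 42 | 48 | 60 | Forms | Origin |
|---|---|---|---|---|---|---|---|---|
| Study design | yes | yes | yes | yes | no | no | 7 | enrolment |
| Follow up | yes | no | yes | no | yes | no | 6 | treatment |
| Appendix 4 | yes | no | yes | no | yes | yes | 7 | not stated |

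The two prose sections disagree at 3 of 8 months (30, 42, 48). With the Appendix 4 row it is 4 of 9.

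On the survival assumptions above, the completion denominator at a disputed month is one of these counts or zero, depending on which section is followed:

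| Month | Arm A | Arm B | Both |
|---|---|---|---|
| 30 | 71 | 53 | 125 |
| 42 | 57 | 38 | 94 |
| 48 | 50 | 32 | 82 |
| 60 | 40 | 22 | 62 |

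Allowing for dropout would lower every count. Arm figures may not add to the total because of rounding.

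**The case against.** The strongest reply is that the objective is only to investigate QoL in both groups. No hypothesis, test or power is stated, and change from baseline with intervals, charts by arm and completion rates is a coherent descriptive plan. That stands, and it is why the point is minor. The proposed contrast should also be labelled descriptive.

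Second, SAP 3.9 can fairly be read as reaching QoL. It commits to linear models for metric outcomes, and with the laboratory marker analysis deferred, QoL scores are the only metric secondary endpoint with a current analysis. So a reader who infers that the SAP has no model for QoL goes too far. What remains is that no arm contrast is named and the baseline score is not a candidate covariate.

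Third, change from baseline is not an error, and an unadjusted difference can be derived if means and intervals are reported per arm, as the charts suggest. The precision gain rests on an assumed correlation. At late visits the comparison is among survivors, where randomised balance is not guaranteed. ANCOVA and change scores may then estimate different quantities, so the variance ratio is not the whole comparison. This stands as a limit on the figures.

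Fourth, the Follow up list and Appendix 4 describe their assessments as recommended, and month 60 depends on reading an extracted table. The second point stands. The first does not remove the conflict: a recommended list still differs from the Study design text, which needs no table to disagree with it.

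**Conclusion.** The concern holds in a limited form, with two parts.

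**Analysis (a cheap improvement).** The SAP names no between-arm QoL difference and does not adjust for the baseline score. Adjustment would narrow the interval by about 8% to 19% for an assumed correlation of 0.7 down to 0.3 with equal variances, among patients alive with both forms.

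**Schedule (wrong as written).** The Study design and Follow up sections contradict each other at months 30, 42 and 48 and on the time origin. Appendix 4 appears to add month 60.

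Two stronger readings are not supported. One is that the baseline is ignored: a change score already uses it. The other is that scales and visits would be picked freely after the data are seen: the endpoints are all the questionnaire scores, and items and subscales are to be charted over time for each arm, so that risk is limited. The absence of named key scales is missing detail rather than an error.

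Priority is low. The primary endpoint and its error control are unaffected.

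**What to change.** **SAP 3.6.3.** For each QLQ-C30 and QLQ-BR23 score at each scheduled QoL visit, add the between-arm difference with 95% CI from an ANCOVA with arm and baseline score as terms. Label it descriptive and conditional on being alive with both forms. Show the numbers alive and the numbers responding, by arm, beside each estimate. Add the matching table to SAP section 4.

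**Protocol and SAP.** Reconcile the Study design section, the Follow up section and Appendix 4 to one QoL visit list and one time origin. Cite that list in the SAP as the denominator for the completion rates.

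**Cost.** SAP text, one protocol clarification and a little programming. The contrast needs no new data. Reconciling the schedule may add or remove forms at months 30, 42, 48 or 60. The downside of the ANCOVA is that patients without both forms drop out, although the SAP's QoL population admits them; the planned change score loses the same patients. QoL remains unpowered and descriptive.
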